10.5.2 Secondary Endpoints

Additional measures will be summarized:

Secondary Safety Endpoint:

- Serious Adverse Events (SAE) associated with the procedure or device
- All serious neurological adverse events **Secondary Performance Endpoint**:
- Detailed assessment of aneurysm occlusion from Post Procedure to 6-months provided by the core lab review of the angiogram (DSA) including the following:
 - Raymond Roy scale
 - Modified Web Occlusion Scale
 - Percent Occlusion
 - Device Stability
- Rate of retreatment
- Summary of device performance including the following:
 - Time required for implantation of the Contour
 - Device sizes used
 - Number of attempts to deploy the device
 - Number of failed implant attempts
 - Any reports of device deficiencies

10.5.3 Independent Analysis of Imaging

Follow-up imaging (i.e., cerebral angiograms) angiographic assessments of the aneurysm shall be completed by an independent core laboratory with experience in neurovascular imaging of IAs. Clinicians responsible for imaging analyses at the core laboratory will not have any financial conflict with the study sponsor and shall not be affiliated with a clinical study site.

| Cerus Endovascular | Document Number DNX099-01 | Rev F | Page 44 of 106 |
|----------------------------|--|---------------|----------------|
| Investigational Protocol | Title | | |
| Confidential & Proprietary | Contour Neurovascular System TM European Pre-M Study (CERUS) | 1arket Unrupt | ured Aneurysm |

10.6 Interim Analysis

No interim data analysis will be performed.

10.7 Sample Size Rationale

This is a single arm study designed to provide adequate data for the purpose of CE Mark. It is expected the 30 patients with evaluable data at 6 month follow-up will show adequate evidence of safety and performance for the application for CE Mark of the device. No formal hypothesis testing of the study endpoints will be performed, therefore no formal sample size was calculated.

11 Additional Trial Characteristics

11.1 Measures Taken to Avoid Bias

The study has been designed to ensure treatment and follow-up of subjects are consistent with current medical practice.

The study will be approved by the central Ethics Committees (ECs) prior to initiation and will undergo continuing review by the ECs as the study progresses. Additionally, each clinical site will provide further oversight and approval of the study.

All investigators must disclose potential conflicts of interest, including financial interests, to the study sponsor prior to participation in the study.

Data from all investigative sites will be monitored throughout the study.

A CEC/DSMB will adjudicate all neurological, device related and procedure related serious adverse events.

A CEC/DSMB will regulatory review the study data to provide oversight and necessary input for any trial modifications.

Imaging obtained during the procedure and follow-up period will be reviewed by an independent Core Laboratory to verify the status of the Contour implant and the surrounding vasculature.

11.2 Special Equipment for Investigation

Apart from the study device, all equipment used in the trial will be maintained and calibrated in accordance with the clinical site institution's policies and procedures.

11.3 Procedure for Replacing Withdrawn Subjects

Subjects who withdraw from the study shall not be replaced.

| Cerus Endovascular | Document Number DNX099-01 | Rev F | Page 45 of 106 |
|----------------------------|--|---------------|----------------|
| Investigational Protocol | Title | | |
| Confidential & Proprietary | Contour Neurovascular System TM European Pre-M Study (CERUS) | 1arket Unrupt | ured Aneurysm |

11.4 Other Devices Used During Study

Several devices are standardly used during endovascular procedures to treat IAs. Other than the investigational implant and implant delivery system, no special devices are required for this study.

11.5 Total Expected Trial Duration

The enrollment period is expected to take 9 months and the follow-up duration is expected to be 6 months to obtain data for the primary analysis. The study population will include 30 subjects enrolled and implanted at up to 10 centers in Europe with evaluable data at 6 months for the analysis for CE Mark. It is expected that the study will take 9 months to enroll the first 30 patients and continue up to 9 months for the initial report for CE Mark.

All patients must be consented prior to performing study related procedures. All patients that provide consent and are implanted will be followed according to the follow-up schedule. Any patient for whom a failed implant attempt is performed will be followed for 1-month or until resolution of any potential device or implanted related adverse events, whichever occurs last.

12 Study Management

This study will be managed according to ISO 14155:2011, the Declaration of Helsinki in its current revision, conditions imposed by local ethics committees (ECs), and any applicable regulatory requirements. For this study, the sponsor will have certain direct responsibilities and may delegate other responsibilities to appropriate consultants and/or contract research organizations (CROs). Together, the sponsor and all related participants will ensure that the study is conducted according to the above standards and all applicable regulations. All personnel to participate in the conduct of this clinical trial will be qualified by training, education and/or experience to perform his or her respective tasks.

12.1 Investigator Responsibilities

This section highlights responsibilities of the principal investigator (PI) at each site regarding this investigation. The PI, i.e., the main investigator at each study site, is responsible for managing day-to-day aspects of the study. The PI will take steps to ensure compliance with the CIP and associated documents and processes. The PI also protects data integrity and the rights, safety and well-being of clinical study subjects.

12.1.1 Disclosure

All investigators must disclose potential conflicts of interest, including financial interests, to the study sponsor, both before and during conduct of the clinical study as well as up to 1 year after the study has completed.

| Cerus Endovascular | Document Number DNX099-01 | Rev F | Page 46 of 106 |
|----------------------------|--|---------------|----------------|
| Investigational Protocol | Title | | |
| Confidential & Proprietary | Contour Neurovascular System TM European Pre-M Study (CERUS) | 1arket Unrupt | ured Aneurysm |

12.1.2 Additional Site Team Members

The site may add new members to the investigational team. Training of new personnel will be documented before new personnel participate in the study. New investigators should disclose potential conflicts, as described in Section 12.1.1.

12.1.3 Communications with EC

The site Principal Investigator (PI) and the site clinical study team are responsible for communication with site ethics committee if required. The Sponsor and/or designee is responsible for communication with central ethics committees if required. The PI will:

- provide the sponsor with copies of any relevant EC communications regarding this CIP
- comply with requirements from the EC regarding the CIP
- obtain written/dated approval/favourable opinion from the site EC, before starting the study or recruiting subjects
- obtain written/dated approval from the site EC before implementing any changes in a CIP amendment
- ensure the timeliness of safety reporting to the site EC
- promptly report deviations from the CIP to the EC that affect the rights, safety or well-being of the subject or the scientific integrity of the CIP
- keep all EC communications in its study file

12.1.4 Informed Consent

The PI is responsible for the informed consent (IC) process in this CIP. The PI will ensure that:

- the IC used for the consent process is the most current IC, has been approved by the EC and is consistent with any requirements imposed by the EC
- the IC process occurs consistent with ISO 14155:2011, and importantly, prior to any procedure specific to the clinical investigation is applied to the subject.
- a copy of the signed/dated IC form is kept in the subject's records
- either he/she or an authorized designee conducts the consent process consistent with ISO 14155

12.1.5 Subject Identification Log

The PI or designee will maintain a log of all subjects enrolled in the study. The log links study identification (ID) numbers to identifying patient information (name, contact information). The log will be housed securely on site.

12.1.6 Compliance with CIP

The PI is responsible for ensuring that his/her site complies with the CIP. The PI will:

| Cerus Endovascular | Document Number DNX099-01 | Rev F | Page 47 of 106 |
|----------------------------|--|---------------|----------------|
| Investigational Protocol | Title | | |
| Confidential & Proprietary | Contour Neurovascular System TM European Pre-M Study (CERUS) | farket Unrupf | ured Aneurysm |

- maintain oversight of the study at the clinical site
- sign an investigator agreement form
- conduct the investigation in compliance with this CIP, applicable sections of ISO 14155:2011, and requirements of the EC to ensure the safety and well- being of study subjects
- create, maintain and make available source documents for study subjects
- not implement any change to the CIP without prior approval from the sponsor, local EC, and (if required) regulatory bodies if required
- not deviate from the CIP, except to maintain the subject's rights, protect the life and physical well-being of a subject in an emergency, or the scientific integrity of the investigation
- document all deviations from the CIP¹³
- ensure that the site has adequate staff and capabilities
- ensure that site equipment used in the study is maintained and calibrated
- ensure the accuracy, completeness and timeliness of study data in CRFs and reports
- allow and support sponsor monitoring and auditing activities
- be available to monitors and the sponsor to address questions during study visits
- be available and support regulatory authorities during audits
- respond in a timely manner to sponsor inquiries
- make reasonable efforts to prevent early withdrawal
- make reasonable efforts to ascertain the reason for early withdrawal

12.1.7 Subject Records

The Investigator will maintain original source documents from which study-related data are derived, which include, but are not limited to:

- Clinic progress notes recording subject's medical history and medications
- Medical charts with operative reports and condition of subject upon discharge
- Medical records regarding AEs, including treatment and clinical outcome
- Results of diagnostic examinations

¹³ The sponsor may also document deviations from the CIP

| Cerus Endovascular | Document Number DNX099-01 | Rev F | Page 48 of 106 |
|----------------------------|--|---------------|----------------|
| Investigational Protocol | Title | | |
| Confidential & Proprietary | Contour Neurovascular System TM European Pre-M Study (CERUS) | farket Unrupt | ured Aneurysm |

- Results of subject questionnaires
- Imaging (such as x-rays, angiograms, CTs, MRIs) as well as any existing reading or interpretation of diagnostic imaging
- Notes of phone calls and/or correspondence indicating investigational site's attempts to follow study subjects at the required follow-up visits until subject's participation in the study is complete or terminated
- Records relating to patient death (e.g., death certificate, autopsy report/terminal medical records)
- Printouts of source data generated by technical equipment (e.g., x-rays, angiograms) must be filed with the patient's records

12.1.8 Subject Accountability

The PI will make reasonable efforts to account for all study subjects, especially those who withdrew. If withdrawal is due to problems with study device safety or performance, the PI will obtain the subject's permission to follow his/her status/condition outside the clinical investigation, if possible.

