7.10 Early Withdrawal

Reasons for subject withdrawal prior to study completion shall be documented. Valid reasons for early study withdrawal include:

- Death
- AE or other medical condition that prevents study participation
- Withdrawal of voluntary consent
- Lost to follow-up (LTF)
- Termination of Study

At least three documented attempts shall be made to contact any subject who is LTF.

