7.12 Premature termination

The Sponsor reserves the right to discontinue the clinical trial/investigation at any stage (e.g. for safety reasons) or reduce the follow-up period with suitable written notice to the Investigator.

Possible reason(s) include:

Sponsor makes a final decision for the early termination of the clinical trial, or per DSMB recommendation

Further product development is cancelled.

Should the clinical trial be discontinued by the Sponsor, subjects will be followed up as per routine hospital practice.

In this case, the Investigator shall return all clinical trial/investigation materials (including devices) to the Sponsor and provide a written statement as to why the premature termination has taken place to the EC (if applicable) and inform subjects still participating to the trial. All applicable Clinical Investigation documents shall be subject to the same retention policy (the Investigators and/or designee(s) will be instructed to retain all study records required by the Sponsor and regulatory authorities in a secure and safe facility, with limited access. All study material shall be stored for at least 10 years or as based on national
| Cerus Endovascular | Document Number DNX099-01 | Rev F | Page 37 of 106 | |
|----------------------------|--|---------------|----------------|--|
| Investigational Protocol | Title | | | |
| Confidential & Proprietary | Contour Neurovascular System TM European Pre-M Study (CERUS) | 1arket Unrupt | ured Aneurysm | |

regulations. The Investigator must request authorization from the Sponsor prior to destroying study records). Sponsor or designee will inform the CA about premature termination of Clinical Trial as per regulatory requirements Study discontinuation:

The Study Completion/Discontinuation Form must be completed when:

- the subject is considered lost to follow-up (per the above definition) before the 12 months follow-up time point has been reached or
- the subject withdraws from the study or
- the Investigator withdraws the subject from the study or
- the subject has completed the study (at last Follow up visit per protocol, the 12 months follow up visit).

The Sponsor shall be notified of the reason for subject discontinuation. The site will provide this information on the Study Completion/Discontinuation Form (e-CRF) and on source documents. Investigators must also report this to their EC if defined by their institution's procedure.

8 Adverse Events

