8.2 Adverse Event Classification

8.2.1 AE Severity:

The severity of an AE is a qualitative judgment of the degree of intensity, as determined by the Investigator or as reported by the subject. The severity of the AE shall be evaluated according to the following scale:

| Cerus Endovascular | Document Number DNX099-01 | Rev F | Page 39 of 106 |
|----------------------------|---|---------------|----------------|
| Investigational Protocol | Title | | |
| Confidential & Proprietary | Contour Neurovascular System [™] European Pre-M Study (CERUS) | 1arket Unrupt | ured Aneurysm |

- Mild no limitation of usual activities, no therapy or only symptomatic therapy required to treat the injury or illness.
- Moderate some limitation of usual activities or specific therapy is required.
- Severe inability to carry out usual activities, hospitalization, emergency treatment, life threatening events, or death.

The assessment of severity shall be made independent of the relationship to the device and therapy or the seriousness of the event.

8.2.2 AE causality:

Each AE shall be assessed by the Investigator for its relationship to the use of the study device or study procedure as outlined below.

Device Related: Restricted to the study device.

Procedure Related: Restricted to the implant procedure and any procedure associated directly with placement of the device.

Definitely related: An AE is definitely related to a specific category if it is obvious, certain or there is little doubt regarding the relationship.

Possible related: An AE is possibly related to a specific category if it is capable of being related but relatively unlikely.

Not related: An AE is not related to a specific category if it is determined that there is no plausible association.

Subjects experiencing AEs shall be offered comprehensive medical care for conditions associated with the implant procedures and followed until their medical outcomes are resolved.

| AEs | Non- DeviceRelated | Device-Related | | Device Deficiencies* |
|-------------|-----------------------|----------------|---------------|------------------------|
| Non-Serious | AE | ADE | | Without SADE potential |
| Serious | SAE | SADE | | With SADE potential |
| | | Anticipated | Unanticipated | |

Table **6**. AE Categorization

| Cerus Endovascular | Document Number DNX099-01 | Rev F | Page 40 of 106 |
|----------------------------|---|---------------|----------------|
| Investigational Protocol | Title | | |

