10.3 General Principles

The analysis for all primary and secondary study endpoints and baseline, procedural and follow-up characteristics will be performed on an intent-to-treat analysis population which will include all available data for all enrolled subjects. Standard summary statistics will be calculated for all study variables.

The primary safety endpoint will be calculated as the proportion of subjects with death of any nonaccidental cause or any major stroke within the first 30 days after treatment or major stroke or death due to neurological case from day 31 to 6 months after treatment.

The primary performance endpoint will be calculated as the proportion of subjects with complete occlusion demonstrated with a Grade 1 on the Raymond Roy Scale at 6 months.

For AE reporting, both subject counts and event counts will be presented in tabular summaries of results.

A summary of subjects with protocol deviations will be reported but those subjects will be included in all analyses although endpoints may be summarized without the subjects (per-protocol analysis group) to provide additional information but not for the primary analysis.

For continuous variables, statistics will include means, standard deviations, medians and ranges. Categorical variables will be summarized in frequency distributions. Missing data will not be imputed. The number of data values available for each analysis will be reported so that the impact of missing data can be seen.

Statistical analyses will be conducted in SAS version 9.4 or above (SAS Institute, Cary, N.C.).

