Two patient populations will be considered in the analyses, an Intent-to-Treat (ITT) population and a Per Protocol population (PP). The ITT population includes all patients. The PP population will include subjects who complete 6 months of follow-up, die prior to their 6-month clinic visit, or are study failure (withdrawal from study to obtain alternate treatment). The PP will exclude patients with any major protocol violation that affects proper study inclusion or significant outcomes. Endpoints will be evaluated in the PP and ITT populations.

Any patient for whom a failed implant attempt is performed will be followed for 1 month, or until resolution of any potential device or implanted related adverse events, whichever occurs last.

Any patient who is consented but has no implant attempt will be study exited.

6 General Statistical Principles

The analysis for all primary and secondary study endpoints and baseline, procedural and follow-up characteristics will be performed on an intent-to-treat analysis population which will include all available data for all enrolled subjects. Standard summary statistics will be calculated for all study variables. For continuous variables, statistics will include means, standard deviations, medians and ranges. Categorical variables will be summarized in frequency distributions. Missing data will not be imputed. The number of data values available for each analysis will be reported so that the impact of missing data can be seen.

Statistical analyses will be conducted in SAS version 9.4 or above (SAS Institute, Cary, N.C.).

Cerus Endovascular	Document Number DNX099-13	Rev A	Page 7 of 9	
Statistical Analysis Plan	Title Statistical Analysis Plan for: Contour Neurovascular System [™] European PreMarket Unruptured Aneurysm Study (CERUS)			
Confidential & Proprietary				

7 Analysis of Study Endpoints

Primary Safety Endpoint

The primary safety endpoint will be calculated as the proportion of subjects with death of any nonaccidental cause or any major disabling stroke within the first 30 days after treatment or major disabling stroke or death due to neurological cause from day 31 to 6 months after treatment.

Where "Major Disabling Stroke" is defined as an episode of neurological signs or symptoms that persist beyond 24 hours accompanied with evidence of ischemia/infarction on imaging that results in an increase of NIHSS from baseline by ³ 4 points and/or an increase from mRS baseline by >2.

Primary Performance Endpoint

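### New events after a device-related withdrawal have no stated route into the study data, so the 6-month safety and retreatment rates can be under-counted

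*Protocol*

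**What the plan says.** Protocol 7.10 lists valid reasons for early withdrawal. One is "AE or other medical condition that prevents study participation". Protocol 7.12 requires a Study Completion/Discontinuation Form in several situations, including when "the Investigator withdraws the subject from the study".

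Protocol 12.1.8 covers what follows. It opens with a general duty: "The PI will make reasonable efforts to account for all study subjects, especially those who withdrew". For withdrawals caused by device safety or performance it then says "the PI will obtain the subject's permission to follow his/her status/condition outside the clinical investigation, if possible".

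Other sections bear on the same subjects:

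- Protocol 8.2.2 says that subjects with AEs are to be offered care and "followed until their medical outcomes are resolved".
- Protocol 12.1.6 has the PI "make reasonable efforts to prevent early withdrawal".
- Protocol 10.3 and SAP 6 set an intent-to-treat analysis that "will include all available data for all enrolled subjects". Missing values are not imputed; the number of available values is reported instead.
- Protocol 10.2 and SAP 5 define the per-protocol set. It takes in subjects who complete 6 months, who die before the 6-month visit, or who "are study failure (withdrawal from study to obtain alternate treatment".
- SAP 7 measures retreatment of the target aneurysm from implant to 6 months. The primary safety endpoint counts major disabling stroke and neurological death from day 31 to 6 months.

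**The concern.** The study exists to document safety and performance for CE Mark. Subjects who leave because of a device problem are unlikely to be a random subset, and they still carry the implant. For these subjects the protocol places further follow-up, by its own words, outside the study, and makes it depend on permission and feasibility.

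If a new stroke, neurological death or retreatment occurs between withdrawal and month 6, the plan does not say that it is recorded, adjudicated or counted. With about 30 subjects, one or two such events change the reported safety picture, and no later analysis can recover data that were never collected.

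**Working it through.** **Step 1. Trace an event that occurs after withdrawal.** Take a subject who withdraws over a device problem in month 2 and has a new stroke, or retreatment of the target aneurysm, in month 4. Each provision that might capture the event is checked in turn.

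- *All available data for all enrolled subjects* (Protocol 10.3, SAP 6): this covers what the study collects. It does not say that follow-up under 12.1.8 is collected.
- *AE collection* (synopsis, Follow-Up and Required Assessments): runs from implantation through study duration. Its position after an individual withdrawal is not stated.
- *Follow AEs to resolution* (8.2.2): applies to the AE already present, not to a new one. For the AE already present, it has to be reconciled with 12.1.8.
- *CEC review* (9.1): the committee can adjudicate only what is reported to it.
- *Per-protocol set* (10.2, SAP 5): keeps the subject in the set but does not supply the later outcome.
- *Retreatment* (SAP 7): defined by a time window, with no statement on whether exit for alternate treatment counts.

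No provision clearly brings the month-4 event in. The plan describes no sensitivity analysis for missing safety outcomes, and it does not fix the safety denominator for subjects who leave event-free before 6 months.

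**Step 2. Reproduce the plan's own figure.** The synopsis allows at most 35 enrolled to obtain 30 with follow-up.

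- Allowed attrition = 35 − 30 = 5 subjects; 5/35 = 14.3%.
- Check: 30/(1 − 5/35) = 35.

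The plan states no attrition rate, so 14.3% is back-calculated and is not an independent reproduction. Protocol 10.7 gives no formal sample size calculation, so there is no power figure to check.

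**Step 3. Illustrate the size.** Let x be the events observed among the 30, and k the uncounted events among the 5 lost. Reported rate = x/30; true rate = (x + k)/35. Both x and k are assumptions. Intervals are exact two-sided 95% Clopper-Pearson; for x = 0 the upper limit is 1 − 0.025^(1/30) = 11.6%.

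| Reported | k | True |
|---|---|---|
| 0/30 = 0% (0 to 11.6%) | 1 | 1/35 = 2.9% (0.1 to 14.9%) |
| 0/30 = 0% (0 to 11.6%) | 2 | 2/35 = 5.7% (0.7 to 19.2%) |
| 0/30 = 0% (0 to 11.6%) | 5 (extreme) | 5/35 = 14.3% (4.8 to 30.3%) |
| 1/30 = 3.3% (0.1 to 17.2%) | 1 | 2/35 = 5.7% (0.7 to 19.2%) |

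If the five were instead kept in the denominator as event-free, the report would be 0/35 with an upper limit of 10.0%, which looks better still.

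**Step 4. Check the direction.** An uncounted event can only lower the numerator. When the five also leave the denominator, the reported rate is too low if x/30 < (x + k)/35, that is 35x < 30x + 30k, or x < 6k. With k = 1 this holds for any observed count below 6. With k = 0 the effect is small and reversed: 1/30 = 3.3% against 1/35 = 2.9%.

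**The case against.** The strongest reply is that 12.1.8 adds protection. It applies to someone who has already withdrawn, and asks the PI to seek permission to keep watching that person. The defaults favour retention: implanted subjects are to complete scheduled follow-up, and the PI must try to prevent withdrawal and account for those who leave. SAEs reach the sponsor within 48 hours, the CEC reviews deaths, and withdrawal reasons are documented, so an exit for alternate treatment would be known. Consent pages and most CRF pages, including the exit form, are not available here, and the Data Management Plan is a separate document. Any of these could deal with data after withdrawal.

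Much of this stands, and it rules out four stronger readings that a reader might infer.

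- *These subjects vanish from the study data.* They do not. The triggering AE and everything before withdrawal remain in the intent-to-treat analysis.
- *Any AE is grounds for withdrawal.* Protocol 7.10 limits this to an AE that prevents participation.
- *SAP 5 makes alternate treatment a forced exit.* It does not. The phrase is an inclusion rule for the per-protocol set.
- *Each missed event belongs among the 30 evaluable subjects, giving 1/30 = 3.3%.* The 30 are those with 6-month data. Subjects lost earlier would normally be additional, hence the denominator of 35.

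The reply does not answer the remaining gap. 12.1.8 is more than silent: it places the follow-up outside the investigation, and neither document says that what is learned there comes back in.

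**Conclusion.** The point holds for new events after withdrawal. When the withdrawal is device-related, the plan as written can miss strokes, neurological deaths and retreatments within the 6-month window, and such a loss is plausibly informative and favourable to the device.

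The size cannot be fixed from the documents. If all 5 subjects allowed for attrition are lost and one or two have an uncounted event, a reported 0% (upper limit 11.6%) would truly be 2.9% (14.9%) or 5.7% (19.2%). The actual number of device-related withdrawals may be zero, in which case nothing is lost. The conclusion also assumes that the consent form, exit form and Data Management Plan do not already provide for this; if they do, the protocol and SAP should say so.

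**What to change.** 1. **Protocol 7.10 and 12.1.8.** Separate stopping study visits or angiography from withdrawing consent to data collection. In 12.1.8, replace follow-up outside the investigation with retention in the study for a minimum data set at 6 and 12 months: vital status and cause of death, stroke, mRS, target-aneurysm retreatment and SAEs. Record it on the eCRF and send it to the CEC, unless the subject withdraws consent to data collection. Reconcile the text with 8.2.2. The 7.10 wording on an AE that prevents participation can stay as a reason to stop visits.
2. **SAP 5 and 7.** Count exit to obtain alternate treatment of the target aneurysm within 6 months as a retreatment. Include permitted post-withdrawal data in the primary safety endpoint.

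The cost is protocol, SAP and consent wording, one short eCRF page and a few telephone contacts. No new procedure is needed. The downside for the sponsor is that the reported safety and retreatment rates may be slightly less favourable.
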